7.1.1 Induction therapy phase

Eligible patients will be randomized before proceeding to 7+3, or within one week of starting 7+3 in 1:1 ratio, to 7+3 alone or 7+3+ Pembrolizumab (MK-3475). As shipment of pembrolizumab to site can only be ordered after randomization, every effort should be done to randomize the patient as soon as possible. See Section 9.1 for agent ordering information. If patient is randomized after initiation of 7+3 therapy, the patient should continue to meet all eligibility criteria up to randomization date. Planned stratification factors include 1) age (younger than 65 vs. 65 and older), 2) cytogenetics **by FISH or metaphase karyotype** (presence vs. absence of core binding factor inversions and translocations), and 3) **t- AML or AML arising from prior/antecedent MDS (yes/no)**. All patients will receive cytarabine at 100 mg/m²/day continuous infusion on Days 1-7 and either idarubicin 12 mg/m²/day IV on Days 1-3 or daunorubicin 60 mg/m²/day IV on Days 1-3. A bone marrow biopsy on Day 14 (between Days 14 and 21) will be performed to assess for chemoablation. If patients have evidence of residual leukemia (defined as per institutional practice) in their bone marrow and following assessment by repeat transthoracic echocardiography (TTE) for assessment of ejection fraction, they will receive re-induction 5+2 chemotherapy, which means patients will receive cytarabine at 100 mg/m²/day continuous infusion on Days 1-5 and either idarubicin 12 mg/m²/day IV or daunorubicin 60 mg/m²/day IV on Days 1-2. Anthracycline dosing adjustments may need to be made, per institutional guidelines. Regardless of chemoablation status, on Day 8 of the induction chemotherapy and Q3W (±3 days) thereafter, half of the patients will receive Pembrolizumab (MK-3475) IV (intervention arm). The other half will not receive Pembrolizumab (MK-3475) (control arm). At time of count recovery, defined as platelet count more than 50,000 or neutrophil count more than 500, patients will undergo a bone marrow aspirate/biopsy in order to assess for response and MRD. If there is no count recovery, a bone marrow will have to be performed by day 42. If the bone marrow shows hypoplasia and patient remains without count recovery, a bone marrow will be performed q 2 weeks (+/- 3 days) till there is count recovery or evidence of persistent AML. If patients have a CR or a CRi, patients will continue with consolidation therapy. If patients do not achieve a CR or CRi, they will be taken off study. If Pembrolizumab is discontinued for any reason (after at least one dose of Pembrolizumab, the patient should continue on 7+3 or Re-Induction on study.

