7.1.2 Consolidation therapy phase

Consolidation therapy will consist of up to four cycles of infusional HiDAC and Pembrolizumab (MK-3475) (intervention arm) vs. HiDAC alone (control arm). Patients <60 years of age will receive 3 g/m² every 10-12 hours (Q12H) on Days 1, 3, and 5 (total 6 doses). Patients ≥60 years of age will receive 1.5 g/m² Q12H on Days 1, 3, and 5 (total 6 doses). Cycle 1 of consolidation therapy must start within 4 weeks of documenting remission status. Each cycle lasts ~28 days (up to 42 days). Patients in the intervention arm will continue to receive MK-3475 (pembrolizumab) Q3W (±3 days). Do not administer pembrolizumab concurrently with HiDAC chemotherapy Days 1-5 of each consolidation cycle. For consideration of timing of pembrolizumab, allow at least 3 hours after completion of chemotherapy prior to pembrolizumab

administration. Administration window for pembrolizumab may be extended to allow for this timing as necessary. After Cycle 1 of HiDAC, bone marrow assessment will be performed at the time of count recovery (same rules apply as post induction bone marrow in case of lack of count recovery) for formal assessment of response and MRD. Patients, who remain in CR or CRi, will be allowed to proceed to up to 3 more cycles of HiDAC and Pembrolizumab (MK-3475) (intervention arm) vs. HiDAC alone (control arm). Patients, who are not in CR or CRi will be taken off study. . If Pembrolizumab (MK-3475) is discontinued for any reason (after at least one dose of Pembrolizumab), the patient should continue Consolidation therapy on study.

Consolidation Therapy Regimen Description					
Agent	Premedications ; Precautions	Dose*	Route	Schedule	Cycle Length
Pembrolizumab (MK-3475) (For Intervention Arm only)	Premedication with antipyretic and antihistamine may be considered. No premedication with steroids	200 mg See Section 8.1 for instructions on the preparation of the infusion solution.	IV over 30 minutes (between 25-40 minutes) using an infusion set containing a low-protein binding 0.2 to 5 µm in-line filter. See Section 8.1 for compatible infusion set materials including in-line filter.	Q3W (±3 days) continuous from Day 8 of Induction. For consideration of timing of pembrolizumab, allow at least 3 hours after completion of chemotherapy prior to pembrolizumab administration	28 days (±7 days)

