7.1.3 Maintenance therapy phase

Following count recovery from the last cycle of consolidation therapy, a bone marrow biopsy will be performed to assess for response and MRD. Patients, who remain in CR/CRi will continue on maintenance therapy while patients who do not remain in CR/CRi will be taken off study. Patients in CR/CRi will proceed with single-agent Pembrolizumab (MK-3475) (intervention arm) vs. no maintenance therapy (control arm) Q3W dosing schedule for up to 2 years, calculated from first day of maintenance therapy, according to their original randomization (*i.e.*, there will be no second randomization). For patients randomized to Arm B, Pembrolizumab (MK-3475) will be administered on Day 1 (+/- 3 days) of each maintenance cycle (each maintenance cycle is 21 days). Bone marrow samples will be obtained every 3 months while

patients are receiving maintenance or in observation to assess for MRD. Patients, who are deemed to require HSCT, can forgo any remaining protocol-defined consolidation or maintenance therapy and proceed with HSCT. Patients proceeding with HSCT will be followed for survival and SAEs through the first 100 days post-HSCT including assessment for occurrence of acute and chronic GVHD.

Maintenance Therapy Regimen Description					
Agent	Premedications ; Precautions	Dose	Route	Schedule	Cycle Length
pembrolizumab (MK-3475) (For Intervention Arm only)	Premedication with antipyretic and antihistamine may be considered. No premedication	200 mg See Section 8.1 for instructions on the preparation of the infusion	IV over 30 minutes (between 25-40 minutes) using an	Day 1(+/- 3 days) of each 21-day maintenance cycle	21 Days

Maintenance Therapy Regimen Description					
Agent	Premedications ; Precautions	Dose	Route	Schedule	Cycle Length
	with steroids	solution.	infusion set containing a low-protein binding 0.2 to 5 µm in-line filter. See Section 8.1 for compatible infusion set materials including in-line filter.		

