7.4 Duration of Follow-Up

Patients will be followed up for survival and remission status for at least every 6 months for up to 5 years after the randomization or until death, whichever occurs first. Patients will be monitored for AE of Special Interest(s) post-transplant for the first 100 days, particularly GVHD and VOD, in both arms. We additionally recommend for the investigators that the patient not receive pembrolizumab within 30 days of receipt of transplant. Patients removed from study for unacceptable AE(s) will be followed until resolution or stabilization of the AE.

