Bone marrow biopsy	X										X ⁿ				X				X ^o		X	X		X ^s				
Stool	X														X ^z													
Research Blood Draws	X									X ^m	X ⁿ				X				X ^o	X ^q	X ^r	X ^r		X ^s				
Skin Punch Biopsy ^α	X																											
Transthoracic ECHO (TTE) or MUGA	X								X ^t																			
CT chest	X ^s																											

- a If the patient does not have a CR/CRi before starting this part of the study, the patient should go off study. Patients <65 may complete 3-4 cycles of consolidation therapy. Patients ≥65 years old may complete 1-2 cycles of consolidation therapy.
- b End of treatment visit will be immediately following final dose of Pembrolizumab (MK-3475).
- c After completing study treatment, clinical follow-up assessments are required every 6 months from date of therapy discontinuation. Common clinical practice should be monitored by institutional practice (*i.e.*, every 3 months though not required by protocol), but assessment results are only required every 6 months (+/- 14 days). All participants should be followed for survival to 3 years after end of treatment. For patients who achieve undetectable MRD during study treatment, central MRD assessments should continue in addition to general clinical follow.
- d Cytarabine should be dosed as appropriate for each phase of the study. Daunorubicin (60 mg/m²/day) or Idarubicin (12 mg/m²/day)
- e If patient has residual leukemia at the time of bone marrow aspiration, the patient may receive a 5+2 administration of these drugs. Adjust anthracycline dose as per institutional standards for Re- Induction.
- f Only for patients randomized to Arm B at 200 mg. Pembrolizumab (MK-3475) will be administered on Day 8 of induction and then Q3 weeks (+/- 3 days). Do not administer pembrolizumab concurrently with HIDAC chemotherapy Days 1-5 of each consolidation cycle. For consideration of timing of pembrolizumab, allow at least 3 hours after completion of chemotherapy prior to pembrolizumab administration. Administration window for pembrolizumab may be extended to allow for this timing as necessary. Each cycle of Maintenance is 21 days with pembrolizumab given on day 1 of each cycle up to 2 years.
- g Note: Performance status evaluations are based on a 4-week cycle. At minimum, performance status should be evaluated at the beginning of every cycle.

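### The protocol gives incompatible survival follow-up horizons and never defines 'off study', so overall survival could be censored informatively if the treatment sections were applied literally

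*Combined protocol and SAP*

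**What the plan says.** **Transplant patients.** Section 7.1.3 states "Patients proceeding with HSCT will be followed for survival and SAEs through the first 100 days post-HSCT". Section 7.4 states "Patients will be followed up for survival and remission status for at least every 6 months for up to 5 years after the randomization". Only an earlier death shortens this, and there is no exception for transplant. Its own 100-day limit covers safety only: "Patients will be monitored for AE of Special Interest(s) post-transplant for the first 100 days", naming GVHD and VOD.

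**Other horizons.** Study Calendar footnote c says "All participants should be followed for survival to 3 years after end of treatment". The follow-up paragraph of Section 10.1 collects survival and disease status for at most three years from first dose. Its next sentence bases the survival and RFS analysis on five-year follow-up from randomization.

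**Patients without CR/CRi.** Four places use the same term:
- Section 7.1.1, after induction: "If patients do not achieve a CR or CRi, they will be taken off study".
- Section 7.1.2, after consolidation cycle 1: "Patients, who are not in CR or CRi will be taken off study".
- Section 7.1.3, after the last consolidation cycle: "patients who do not remain in CR/CRi will be taken off study".
- Study Calendar footnote a: "If the patient does not have a CR/CRi before starting this part of the study, the patient should go off study".

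The term is not defined. Section 7.3 requires the reasons and dates for stopping therapy and for study removal to be documented as separate items.

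**Endpoint.** Section 1.2.5 measures OS from randomization to death from any cause. Section 10.1 censors patients who are alive at the end of follow-up, or lost to it, at the date last known alive.

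**The concern.** A site needs one answer to how long it follows a randomized patient for survival. The protocol gives several, and the answer can depend on whether the patient responded or went to transplant. Because OS is censored at the date last known alive, follow-up that stops early becomes a censored observation.

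If stopping depends on treatment failure, the censoring is tied to a strong predictor of early death, and Kaplan-Meier no longer estimates survival of the randomized population. The between-arm comparison is exposed too, because the trial's premise is that response differs by arm. Part of any survival gain that comes through better response would be hidden. The five-year RFS analysis needs relapse status over the same period.

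Separately, data collected for only three years cannot support a five-year analysis, whatever sites do with the treatment sections.

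**Working it through.** **1. The plan's stated figure.** No power, sample size or event count is given for OS. The primary comparison has 25 per arm, 50% versus 75%, one-sided alpha 0.1. With pooled variance under the null, the standard errors are √(2 × 0.625 × 0.375/25) = 0.1369 (null) and √(0.25/25 + 0.1875/25) = 0.1323 (alternative). Power = Φ[(0.25 − 1.2816 × 0.1369)/0.1323] = Φ(0.563) = 0.713, which reproduces the stated 71%. This endpoint is binary and read after consolidation cycle 1, so the survival horizon does not touch it.

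**2. The horizons side by side** (months from randomization, 30.4375 days per month; first dose taken as about the time of randomization).

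| Patient | 7.1.x read literally | 10.1 collection | Footnote c | 7.4 |
|---|---|---|---|---|
| Induction non-responder, day 42 | 42/30.4375 = 1.4 | 36 | 1.4 + 36 = 37.4 | 60 |
| HSCT at month 4 (assumed) | 4 + 100/30.4375 = 7.3 | 36 | 4 + 36 = 40 | 60 |
| Full treatment | – | 36 | 66 to 68 | 60 |

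For full treatment, end of treatment is at 42 + 28 + 4 × 28 + 730.5 = 912.5 days (30.0 months), or 968.5 days (31.8 months) with 42-day consolidation cycles. Footnote c is therefore shorter than Section 7.4 for early failures and longer for completers.

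**3. Illustration for non-responders.** The documents give no survival medians by response, so these are assumptions: CR/CRi 60–80%, median OS 4–9 months without CR/CRi and 24–36 months with it, exponential survival, failures censored at t₀ = 42 days = 1.38 months. Let c be the CR/CRi rate, and S_r and S_n survival of responders and non-responders.
- True: S(24) = c·S_r(24) + (1 − c)·S_n(24).
- Censored: S*(24) = [c·S_r(t₀) + (1 − c)·S_n(t₀)] × S_r(24)/S_r(t₀).

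Worked example with medians of 30 and 6 months: S_r(24) = 2^(−24/30) = 0.574; S_n(24) = 2^(−24/6) = 0.0625.
- c = 0.80: true 0.8 × 0.574 + 0.2 × 0.0625 = 0.472; censored 0.945 × 0.593 = 0.561.
- c = 0.65: true 0.65 × 0.574 + 0.35 × 0.0625 = 0.395; censored 0.928 × 0.593 = 0.550.

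The true difference between these two rates is 7.7 points; after censoring it is 1.0. Over the whole assumed range, 24-month OS is overstated by about 6 points (c = 0.80, medians 9 and 24) to about 20 points (c = 0.60, medians near 5 and 36).

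**4. Illustration including transplant.** This is a Kaplan-Meier simulation of 400,000 patients with other assumptions: non-response 20–40%, non-responder median 8 down to 4 months, responder median 30 months, no deaths before 1.4 months, HSCT at 4.5 months in 28% of responders still alive, hazard ratio 0.7 after HSCT. The 28% borrows 9 of 32 patients from the frontline nivolumab trial cited in the background.

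| 24-month OS | 20% non-response, median 8 | 30%, median 6 | 40%, median 4 |
|---|---|---|---|
| Full five-year follow-up | 0.523 | 0.454 | 0.378 |
| Non-responders censored | 0.619 (+0.10) | 0.617 (+0.16) | 0.616 (+0.24) |
| HSCT censored at day 100 only | 0.490 (−0.03) | 0.417 (−0.04) | 0.342 (−0.04) |
| Both | 0.598 | 0.596 | 0.597 |

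Deaths observed by five years per 50 patients fall from 38–41 with full follow-up to 17–23 with both rules. Varying the 30%/6-month case, the HSCT-only effect is −2.3 points if HSCT does not change the hazard (0.437 to 0.414) and −7.7 points if half of responders are transplanted (0.467 to 0.390). In the borrowed trial, 9 of its 23 patients with CR/CRi would be 39% if all transplants were in responders, so the share is a sensitive input.

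**The case against.** The strongest reply is that the protocol does not tell anyone to censor these patients. Section 7.4 covers all patients with no exception for transplant or non-response, and it confines 100 days to adverse events of special interest. Footnote c covers all participants, the calendar has a survival-status row, and Section 10.1 has no censoring rule for patients who go 'off study'. Section 7.4 also continues follow-up for patients removed from study for unacceptable adverse events, so removal does not always end contact. Reading 'off study' as off protocol treatment fits much of the document.

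Most of this stands. A reader might infer that the plan as written censors OS informatively; the documents do not support that, because the bias arises only if a site follows the treatment sections and disregards Section 7.4 and footnote c. For non-responders the defect is an undefined term, not a proven contradiction. A reader might also attach the 6 to 24 points to the transplant sentence. That range belongs to the non-responder reading, and the transplant effect runs the other way under the assumptions used. Day 42 is not a fixed exit either, since Section 7.1.1 allows repeat marrows every two weeks in hypoplastic patients without count recovery.

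It is also fair that OS is secondary and unpowered. Near 50% survival, the standard error of a 24-month difference is √(2 × 0.25/25) = 0.14, so the 7.7-point example could not be resolved even with complete follow-up.

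Two things survive. Section 7.1.3 names survival, not only SAEs, within its 100 days, which contradicts Section 7.4. And Section 7.4 cannot simply be taken as governing while Section 10.1 and footnote c set different horizons.

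**Conclusion.** The point holds as an inconsistency with a conditional consequence. The horizons of 100 days post-HSCT, three years from first dose, three years after end of treatment and five years from randomization cannot all be met, and the three-year collection limit contradicts the five-year analysis within a single paragraph. 'Off study' is undefined for the patients whose survival data matter most.

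If the treatment sections were applied literally, censoring non-responders at about day 42 would overstate 24-month OS by roughly 6 to 24 points across the two sets of assumptions. Censoring HSCT patients at day 100 would lower it by about 3 to 4 points with a beneficial transplant in 28% of responders, and by more if transplant is commoner. These figures rest on assumed medians, exponential survival and an assumed transplant share. They show direction and order of magnitude and do not forecast what will happen in this trial. The primary endpoint and its 71% power are unaffected. This should be corrected, but it does not threaten the main result.

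**What to change.** - Reconcile Sections 7.1.1 to 7.1.3, 7.4 and 10.1 and Study Calendar footnotes a and c to one survival horizon, counted from randomization, applying to every randomized patient and long enough for the planned five-year analysis.
- Define 'off study' as distinct from stopping therapy. State that neither going 'off study' for lack of CR/CRi nor proceeding to HSCT ends survival and relapse follow-up.
- Limit the 100-day window in Section 7.1.3 to post-transplant safety monitoring (SAEs and adverse events of special interest, including GVHD and VOD), in line with Section 7.4.

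Whether patients without CR/CRi may remain on treatment is a separate matter. The 'off study' statements conflict with the stable-disease note in Section 13.2.8, which leaves continuation to the investigator. The sponsor must reconcile those passages; no rule is proposed here.

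The cost is wording, plus follow-up contacts that Section 7.4 already requires.

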7.1.4 CTEP IND Agent

Trial treatment of Pembrolizumab (MK-3475) will be administered Q3W starting on Day 8 of

the first induction cycle of the study. Trial treatment may be administered up to 3 days before or after the scheduled day due to administrative reasons.

Note: Dosing interruptions are permitted in the case of medical/surgical events or logistical reasons (*i.e.*, elective surgery, unrelated medical events, patient vacation, holidays) not related to study therapy. Patients should be placed back on study therapy within 3 weeks of the scheduled interruption. If interruption is longer than 3 weeks, patient can resume study therapy with study chair approval. The reason for interruption should be documented in the patient's study record.

Pembrolizumab (MK-3475) will be administered as a dose of 200 mg using a 30-minute IV infusion. Infusion timing should be as close to 30 minutes as possible; however, a window of -5 minutes and +10 minutes is permitted (*i.e.*, infusion time is 25-40 minutes).

7.2 General Concomitant Medication and Supportive Care Guidelines

The study team should check a frequently-updated medical reference for a list of drugs to avoid or minimize use of. Appendix C (Patient Clinical Trial Wallet Card) should be provided to patients.

7.2.1 Pembrolizumab (MK-3475) Concomitant Medication

Medications or vaccinations specifically prohibited in the exclusion criteria are not allowed during the ongoing trial. If there is a clinical indication for any medication or vaccination specifically prohibited during the trial, discontinuation from trial therapy or vaccination may be required. The investigator should discuss any questions regarding this with CTEP. The final decision on any supportive therapy or vaccination rests with the investigator and/or the patient's primary physician; however, the decision to continue the patient on trial therapy or vaccination schedule requires the mutual agreement of the Investigator, CTEP, and the patient.

Acceptable Concomitant Medications

All treatments that the investigator considers necessary for a patient's welfare may be administered at the discretion of the investigator in keeping with the community standards of medical care. All concomitant medication will be recorded on the case report form (CRF) including all prescription, over-the-counter (OTC), herbal supplements, and IV medications and fluids. If changes occur during the trial period, documentation of drug dosage, frequency, route, and date may also be included on the CRF.

All concomitant medications received within 30 days before the first dose of trial treatment and 30 days after the last dose of trial treatment should be recorded. Concomitant medications administered after 30 days after the last dose of trial treatment should be recorded for serious AEs (SAEs).

Prohibited Concomitant Medications

Patients are prohibited from receiving the following therapies during the Screening and Treatment Phase (including retreatment for post-complete response relapse) of this trial:

- Anti-leukemia Immunotherapy not specified in this protocol.
- Anti-leukemia Chemotherapy not specified in this protocol. Note: If patient needs intrathecal chemotherapy after start of trial therapy on study as prophylaxis or for new development of CNS leukemia, patient is allowed to continue on study.
- Investigational anti-leukemia agents other than Pembrolizumab (MK-3475).
- Radiation therapy
 - o Note: Radiation therapy to a symptomatic solitary lesion or to the brain may be considered on an exceptional case by case basis after consultation with study chair and CTEP. The patient must have clear measurable disease outside the radiated field. Administration of palliative radiation therapy will be considered clinical progression for the purposes of determining PFS.
- Live vaccines within 30 days prior to the first dose of trial treatment and while participating in the trial. Examples of live vaccines include, but are not limited to, the following: measles, mumps, rubella, chicken pox, yellow fever, rabies, Bacillus Calmette–Guérin (BCG), and typhoid (oral) vaccine. Seasonal influenza vaccines for injection are generally killed virus vaccines and are allowed; however, intranasal influenza vaccines (*e.g.*, Flu-Mist®) are live attenuated vaccines, and are not allowed.
- Once on and during the treatment phase of the trial, high dose systemic steroid therapy should be avoided as much as possible but is not strictly prohibited.

Patients who, in the assessment by the investigator, require the use of any of the aforementioned treatments for clinical management should be removed from the trial except if they are allowed to continue on study on case-by-case basis based on consultation with study chair and CTEP. Patients may receive other medications that the investigator deems to be medically necessary.

The Exclusion Criteria describe other medications which are prohibited in this trial. There are no prohibited therapies during the Post-Treatment Follow-up Phase.

